#### **10.4 Time Windows for Completing Study Visits**

The time windows within which study visits must occur are shown in Table 10.1. Time is measured from the date of the T1 for Follow-up Study Visits. All visits should be completed as close as possible to the expected date of the visit per the appointment schedule. In monitoring adherence to the protocol, the proportion of visits from each clinic that fall within 2 weeks of the ideal date is reported.

#### **10.4.1 Missed Visits**

If any Follow-up Visit is missed and, for whatever reason, cannot be rescheduled within the permissible time limits for the visit, a notation that a visit has been missed should be noted on the TRTT website and a Missed Visit/Forms Form completed.

Whenever a Study Participant misses a scheduled study appointment, the Clinical Coordinator should contact him or her immediately and arrange another appointment so that the follow-up visit occurs within the permissible time window. If, at any time, the Study Participant cannot be located (which is unlikely for military personnel), an intensive search should be instituted by the Clinical Center immediately, even if the Study Participant has not missed a visit. The Clinical Center should use all available resources to locate the Study Participant, including writing or telephoning each of the contacts listed on the Patient Locator Form. Because this search may be long and time-consuming, it is important that this search be started as soon as any member of the Clinical Center staff is aware that there is a problem. The steps taken to locate the Study Participant should be documented. Experience has shown that with sufficient ingenuity and effort it is almost always possible to find missing Study Participants. When all avenues have been exhausted by the Clinical Center staff and the Study Participant has not been located, the Study Chair should be notified and the procedures outlined in Section 10.4.2 (Inactive Study Participants) followed.

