## **2.2 Design of the Study**

The TRTT involves participants with debilitating tinnitus and functionally normal hearing who would not routinely use or benefit from hearing aids. Participants will be randomized to one of three treatment groups. The goal is to enroll 76 participants per treatment group for a total of 228 Study Participants. Individuals meeting the eligibility criteria will have an equal probability of being randomized to one of the three treatment groups. The randomized schedule will be stratified by Clinical Center. Within each stratum, allocations will be balanced across treatment groups within blocks of consecutive patients. Blocks will be randomly permuted multiples of 3.

Details of the treatment protocols are provided in Chapter 11, 12, and 13. Scheduled study follow-up visits are the same for all treatment groups. These visits will be at 3, 6, 12, and 18 months following the initial treatment visit, and annually thereafter until study close-out. Details of patient visits and examinations are provided in Chapter 10.

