An appointment schedule will be generated following completion of T1. After entering the date T1 was completed, the TRTT online system will automatically generate a schedule for Study Participant treatment with time windows to allow flexibility in scheduling appointments. This schedule also will be available on the TRTT website immediately after following entry of forms associated with T1.

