### **5.8 Entry into the Study**

During the Randomization Visit, ***official study entry into the TRTT occurs by request and receipt of the treatment assignment*** during the interactive internet randomization process, as indicated earlier in this chapter. At this Randomization Visit, informed consent is affirmed, and both the Study Participant and Clinical Center staff are officially committed to the TRTT protocol and procedures for this individual.

***After official study entry has occurred, at the time of treatment assignment, the Clinical Center staff are responsible for following the Study Participant until the study is officially closed.*** This responsibility continues even if, at the last minute, the Study Participant refuses to be treated or fails to return for one or more follow-up visits.

---

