## **10.3 Follow-up Visits**

Follow-up Visits will take place at 3, 6, 12, and 18 months after T1, and then annually until study close-out. Study Participants in all groups are seen at all Follow-up Visits. All Follow-up Visits involve reinforcement counseling as needed.

The Clinical Coordinator or the blinded Study Audiologists (i.e., the Clinical Center Study Audiologist who is not involved in counseling the Study Participant) will complete the Follow-up Medical History Form at each follow-up visit, and ask each participant to complete the following data collection instruments: the Tinnitus Questionnaire, Tinnitus Handicap Inventory, Tinnitus Functional Index, and the Beck Depression Inventory Fast Screen at each Follow-up Visit.

The Follow-up TRT Interview and a full audiological/tinnitus/hyperacusis evaluation, consisting of audiometric pure tone, speech recognition threshold, tinnitus pitch and loudness match, loudness discomfort level (LDL), and word recognition testing will be completed at the 6, 12 and 18 months visit. In addition, the following forms will also be completed at the 6 and 18 month study visits: the Digit Symbol Substitution Test, Hearing Handicap Inventory, State Trait Anxiety Inventory, Positive and Negative Affect Schedule Life Events Checklist, and EuroQOL. It is important that the Study Audiologist who is **not counseling the Study Participant** perform these activities to preserve blinding when measuring these outcomes (see Table 10.2 ).

Note that LDL is checked at all follow up visits. At T2 and the 3 month follow-up visit (F1), the LDL is recorded on the LDL Assessment for Treatment Form for each participant, and at the 6, 12, and 18 months visits, it is recorded on the Audiological/Tinnitus/Hyperacusis (ATH) Examination. LDL testing at these visits is completed by the blinded study Audiologist who is not involved in the treatment of the Study Participant, but the counseling Audiologist may use the LDL results for treatment.

All follow-up visits past 18 months follow-up include only the tinnitus specific health-related quality of life instruments are collected (i.e, the Tinnitus Questionnaire, Tinnitus Functional Index, and Tinnitus Handicap Inventory). These forms may either be completed in person or mailed and returned by post. An in-person visit is not required.

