#### **10.4.2 Inactive Study Participants**

Any Study Participant who has missed two consecutive visits is considered to be inactive, or lost to follow-up until she or he is seen by a study staff member for a complete study visit and is reinstated. The Clinical Center staff is not relieved of responsibility for "inactive" Study Participants. On the contrary, such Study Participants generally require much more staff time than those following the regular schedule. The requirements for managing inactive Study Participants are:

- The Study Participant should be contacted at least every three months. At this time, his or her situation should be reviewed, and if possible, arrangements should be made for him or her to return to the Clinical Center;
- If possible, the Study Participant will be requested to complete the self-test instruments using paper forms that can be mailed to him or her.
- If a Study Participant cannot be located, it is the responsibility of the Clinical Center Director to notify the Study Chair in writing, reviewing in detail the Study Participant's situation and the measures that have been taken to assure adequate

follow-up. The Steering Committee reviews the Study Participant's record and formulates recommendations for action to be taken.

- It is the responsibility of the Clinical Center Director to send written notification to the Study Chair (and a copy to the Director of the Data Coordinating Center (DCC)) outlining the steps taken to locate the Study Participant.

Every effort should be made to encourage an inactive Study Participant to return. If an inactive Study Participant is persuaded to resume clinic visits, the follow-up visit indicated on the Appointment Schedule (as appropriate for that time period) should be completed for this Study Participant. Receipt by the DCC of a Follow-up Visit form completed by Clinical Center staff automatically removes the Study Participant from the inactive category.

All pertinent facts concerning the interim history since the participant's last completed Follow-up Visit should be summarized under the appropriate items on the first Follow-up Visit form which is completed following reinstatement.

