**B. Follow-up Visits**

Visit Number *	Visit Acronym	Target time from T1	Permissible time window
Follow-up Visit 1	(F1)	3 months	>10 weeks to 4½ months
Follow-up Visit 2	(F2)	6 months	>4½ months to 9 months
Follow-up Visit 3	(F3)	12 months	>9 months to 15 months
Follow-up Visit 4	(F4)	18 months	>15 months to 21 months
Follow-up Visit 5	(F5)	30 months	>24 months to 36 months
Follow-up Visit 6	(F6)	42 months	>36 months to 48 months
Follow-up Visit 7	(F7)	54 months	>48 months to 60 months

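### A reachable participant who misses one follow-up visit outside the 10.8 special problems is not sent the TQ by post, and a randomized participant without T1 has no stated follow-up dates

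*Combined protocol and SAP*

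**What the plan says.** **One missed visit.** Section 10.4.1 asks the coordinator to contact the participant at once and rebook inside the window. "If any Follow-up Visit is missed and, for whatever reason, cannot be rescheduled within the permissible time limits for the visit", the miss is noted on the website and a Missed Visit/Forms Form is completed. The section mentions no mailed questionnaire.

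**Two missed visits.** Section 10.4.2: "Any Study Participant who has missed two consecutive visits is considered to be inactive". Paper forms may then be mailed, if possible.

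**Special problems.** Section 10.8 covers participants who move, are deployed or become debilitated. As a minimum they are mailed the TQ, the Tinnitus Functional Index (TFI) and the Tinnitus Handicap Inventory (THI), with a return envelope.

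**After 18 months.** Section 10.3 says of the same three questionnaires: "These forms may either be completed in person or mailed and returned by post".

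**Clock.** Section 10.4: "Time is measured from the date of the T1 for Follow-up Study Visits". Section 5.5: "An appointment schedule will be generated following completion of T1". Table 10.1 gives the 18-month visit the window ">15 months to 21 months", and the 30-month window opens after 24 months.

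**Duty to follow and include.** Section 5.5 requires every randomized participant in the primary analyses. Section 5.8 requires staff to follow each one until close-out: "This responsibility continues even if, at the last minute, the Study Participant refuses to be treated".

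**The concern.** The TQ is a paper self-report form that the plan already accepts by mail in other circumstances. Under 10.4.1 as written, someone who would return it by post, but cannot attend within the window, is recorded as missing. At month 18 no later rule repairs this in time.

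The T1 gap concerns a different person: one who is randomized and then refuses or never attends treatment. The plan requires that person to be followed and analysed, but every follow-up window is counted from an event that did not happen. Without dates no visit can formally be missed, so the two-miss rule in 10.4.2 has nothing to act on.

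At stake are obtainable 18-month scores in the first case and possibly all post-baseline scores in the second. Section 4.4.5 itself warns that dropout may cause serious bias.

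**Working it through.** **1. Routes to a mailed TQ for visits up to month 18**

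| Situation | Section | TQ mailed? |
|---|---|---|
| One missed visit, participant reachable, no special problem | 10.4.1 | No: rebook in window, otherwise log the miss |
| Participant cannot be located | 10.4.1, leading to 10.4.2 | 10.4.2 procedures, without waiting for a second miss |
| Two consecutive misses | 10.4.2 | Yes, if possible |
| Moved, deployed, debilitated | 10.8 | Yes, as a minimum; no two-miss condition |

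Only the first row lacks a postal step.

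**2. Timing at month 18 (Table 10.1, months from T1)**

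- If month 18 is the first miss, inactive status also needs a missed 30-month visit. That window closes at 36 months, which is 36 − 21 = 15 months after the 18-month window closed.
- If months 12 and 18 are both missed, inactive status arises only as the 18-month window closes, at 21 months.
- Between 21 and 24 months (24 − 21 = 3 months) no window is open.

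**3. What a missed month 18 removes**

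- Sections 2.1 and 2.2.3 define the primary outcome as TQ change assessed longitudinally at 3, 6, 12 and 18 months. Section 2.4 plans repeated-measures GEE. Three of four follow-up scores remain.
- Section 2.2.3 calls the 18-month TRT versus SC comparison a secondary analysis; section 9.3.1.1 calls the 18-month change an additional primary outcome. These conflict.
- Section 2.3 bases the sample size on the 18-month time point alone.
- Section 2.2.3 assumes a linear treatment effect over time. As an illustration, assume independent errors of equal variance, so that a participant's information on slope is the sum of squared deviations of the visit times. For 3, 6, 12, 18 (mean 9.75): 45.56 + 14.06 + 5.06 + 68.06 = 132.75 (unrounded sum). For 3, 6, 12 (mean 7): 16 + 1 + 25 = 42. The loss is 1 − 42/132.75, about 68%.

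**4. The plan's own power figures**

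Inputs from sections 2.2 and 2.3: "The goal is to enroll 76 participants per treatment group for a total of 228 Study Participants"; 10% attrition; two-sided 0.05 shared among three comparisons; 80% power for 7 points and more than 95% for 10. The SD is not in the chapters available. Assumed: equal split, alpha = 0.05/3 = 0.0167, z = 2.394.

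- n per arm = 76 × 0.9 = 68.4.
- SD implied by 80% at 7 points = 7 × √(68.4/2) / (2.394 + 0.842) = 12.65.
- Power at 10 points = Φ(10 / (12.65 × √(2/68.4)) − 2.394) = 98.7%, in line with the stated figure. With alpha 0.05 unsplit, the implied SD is 14.61 and the power at 10 points 97.9%.

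The two stated powers agree with each other. The 80% is not an independent check, because the SD was solved from it.

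Power of an 18-month-only analysis under assumed missingness (SD 12.65, alpha 0.0167):

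| Missing at month 18 | n per arm | 7 points | 10 points |
|---|---|---|---|
| 10% | 68.4 | 80.0% | 98.7% |
| 15% | 64.6 | 77.4% | 98.2% |
| 20% | 60.8 | 74.4% | 97.5% |
| 30% | 53.2 | 67.7% | 95.4% |

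Each 1% missing is 0.01 × 228 = 2.28 values.

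**5. No T1**

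- T1 is timed from randomization (0 to 2 months, extendable by the Steering Committee). T2 and all follow-up visits are timed from T1.
- Section 5.5 says the schedule is generated after T1; section 10.2 says it is re-generated then, which implies an earlier one. Neither gives dates for someone with no T1.
- Refusing treatment is not among the 10.8 examples.
- Scale, with assumed inputs: if 5% of one arm (0.05 × 76 = 3.8 people) had no post-baseline TQ and differed by 10 points from the rest, that arm's mean would shift by 0.05 × 10 = 0.5 points.

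**The case against.** The strongest reply is that the uncovered group is small. Section 10.4.1 requires immediate contact, the 18-month window is six months wide, and 10.8 covers the obvious military reasons for absence, introducing its examples as inclusions rather than a closed list. People who cannot be located go to the 10.4.2 procedures without a second miss. All of this stands. A reader might infer that the plan never pursues a missed TQ by post; these sections show otherwise. The person left over is reachable, outside 10.8, and not rebooked in time. The documents do not say how many there would be.

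A reader might also infer that missing month 18 leaves no primary outcome. It does not, because the primary analysis is longitudinal and uses the earlier scores.

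It is tempting to argue that standard of care (SC) participants will drop out more because they get no counseling. The documents do not support that. Section 6.3.1.1 (Question 18) refers to standard of care counseling. Section 10.2 gives SC a consultation, and a T2 visit to equalize contact. Section 10.3 provides reinforcement counseling as needed at follow-up visits. SC participants do know their assignment, so loss related to arm is possible, but no direction or size is given.

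Nor is a TQ from months 21 to 24 shown to be discarded. Section 10.5.1 lets data from non-study visits reach the coordinating center. The gap is that the TQ is assigned to no visit.

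Finally, 10% attrition is already in the sample size, and section 2.3 calls its single-time-point calculation conservative. The power table therefore shows sensitivity, not a demonstrated shortfall.

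**Conclusion.** The point holds in two limited parts, and both should be fixed.

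- Section 10.4.1 has no postal step for a single missed visit by a reachable participant outside 10.8. At month 18 the later rules come too late. The loss is the 18-month value, not the participant's whole contribution to the primary analysis.
- No section available gives follow-up dates to a randomized participant without T1. That person could have no post-baseline TQ, despite the inclusion rule in 5.5 and the follow-up duty in 5.8.

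The size cannot be taken from the documents. The SD of about 12.6, the equal alpha split, the missingness rates, the 5% without T1, the 10-point difference and any differential loss are assumptions. Under them, extra missingness mainly erodes the 7-point component comparisons; the 10-point comparison keeps more than 95% power even at 30% missing. For that comparison the issue is possible bias, which is unquantified.

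Only the manual's first part, into Chapter 11, was available. Chapters 14 (forms) and 23 (analysis) may add handling rules, though no analysis rule restores a TQ that was never collected.

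**What to change.** 1. **Section 10.4.1.** For any 3 to 18-month visit not completed or firmly rebooked, mail the TQ, TFI and THI with a return envelope before the window closes. If both a mailed and a clinic-completed form come back, the clinic form takes precedence.
2. **Table 10.1.** Record a TQ dated between 21 and 24 months as late 18-month data, with its actual date.
3. **Sections 5.5, 10.2 and 10.4.** If T1 has not occurred by the end of the 2-month window, or of any Steering Committee extension, date the outcome assessments from randomization. Reconcile the two descriptions of when the appointment schedule is first produced.
4. **Sections 2.2.3 and 9.3.1.1.** State once whether the 18-month difference is primary or secondary.

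The cost is postage, one scheduling rule in the web system and wording in Chapters 2, 5, 9 and 10. Some TQs will be completed at home, which the plan already accepts. No treatment procedure changes.

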#### **10.4.2 Inactive Study Participants**

Any Study Participant who has missed two consecutive visits is considered to be inactive, or lost to follow-up until she or he is seen by a study staff member for a complete study visit and is reinstated. The Clinical Center staff is not relieved of responsibility for "inactive" Study Participants. On the contrary, such Study Participants generally require much more staff time than those following the regular schedule. The requirements for managing inactive Study Participants are:

- The Study Participant should be contacted at least every three months. At this time, his or her situation should be reviewed, and if possible, arrangements should be made for him or her to return to the Clinical Center;
- If possible, the Study Participant will be requested to complete the self-test instruments using paper forms that can be mailed to him or her.
- If a Study Participant cannot be located, it is the responsibility of the Clinical Center Director to notify the Study Chair in writing, reviewing in detail the Study Participant's situation and the measures that have been taken to assure adequate

follow-up. The Steering Committee reviews the Study Participant's record and formulates recommendations for action to be taken.

- It is the responsibility of the Clinical Center Director to send written notification to the Study Chair (and a copy to the Director of the Data Coordinating Center (DCC)) outlining the steps taken to locate the Study Participant.

Every effort should be made to encourage an inactive Study Participant to return. If an inactive Study Participant is persuaded to resume clinic visits, the follow-up visit indicated on the Appointment Schedule (as appropriate for that time period) should be completed for this Study Participant. Receipt by the DCC of a Follow-up Visit form completed by Clinical Center staff automatically removes the Study Participant from the inactive category.

All pertinent facts concerning the interim history since the participant's last completed Follow-up Visit should be summarized under the appropriate items on the first Follow-up Visit form which is completed following reinstatement.

## **10.5 Other Contact with Study Participants**

### **10.5.1 Unscheduled Visits to the Clinical Center**

In certain cases, the Study Audiologist or Clinical Director may decide that it is in the Study Participant's best interest to return for additional visits beyond the follow-up visits required by the study protocol. Study Participants who experience difficulties also may call and request such visits. The Study Participant may be scheduled for a non-study visit at any time at the discretion of the Study Audiologist. The information obtained at non-study visits should be collected and submitted to the DCC as an Unscheduled Visit., recorded either on the usual data collection forms, or on an Unscheduled Contact Form.

### **10.5.2 Telephone Contacts between Visits**

Maintaining contact with the Study Participant between visits to the clinic has been demonstrated to be an important aspect of continued Study Participant interest and satisfaction. All Study Participants are to be called by the Clinical Coordinator at the midpoint between each follow-up visit or as deemed necessary for effective counseling by the Study Audiologist.

Clinical Coordinators should call any Study Participant more frequently if deemed necessary to maintain this Study Participant's cooperation.

## **10.6 Transfer Study Participants**

If any Study Participant expects to move from the area served by the Clinical Center in which he or she is enrolled, the Study Audiologist caring for the Study Participant should determine whether it is feasible for the Study Participant to travel to any other TRTT Clinical Center for follow-up care. If the Study Participant's new location is expected to be within a reasonable distance of another Clinical Center, the Study Participant should be given the name and telephone number of the Center Director and Clinical Coordinator of that Clinical Center, and the original Clinical Coordinator should schedule an appointment for transferring the Study Participant at the new Clinical Center. Before the Study Participant moves, the Clinical Coordinator should update the Patient Locator Form. After contact with the new Clinical Center has been made, and an appointment has been scheduled, the original Clinical Center should forward copies of all the Study Participant's records to the new Clinical Center. When the Study Participant has been seen once in the new Clinical Center, the DCC transfers the Study Participant officially to that Clinical Center. At that time, the new Clinical Center becomes responsible for following the Study Participant. The Study Participant's I.D. number will change at the time of transfer to reflect that the second Clinical Center is responsible for treating and seeing the transferred Study Participant.

If a Study Participant will be away from their primary Clinical Center during the allowable time window for the next scheduled visit and if they are in the vicinity of another Clinical Center, then such participants may be temporarily transferred to the second Clinical Center. In this case, the primary Study Audiologist should write a letter summarizing the Study Participant's history and present status to the Study Audiologist of the second Clinical Center where the Study Participant is to be seen. Audiological data may be sent with this letter if indicated for the Study Participant's care. The Clinical Coordinator should call ahead and schedule an appointment for the Study Participant. In the case of a temporary transfer, the Study Participant's entire record does not need to be sent; a letter will suffice.

A copy of the correspondence between the Clinical Centers regarding all transfer Study Participants should be sent to the DCC after removing all identifying information.

